Appendix C: Surveillance Protocols

Table C1: Surveillance protocol for incidental nodules, Group A, more intensive surveillance

Patient and Nodule characteristics		Surveillance times (months from index CT)
Solid, with Risk Factors		
≤4		12
>4 to ≤6		6, 18
>6 to ≤8		3, 9, 21 to 24
>8		3, 9, 21 to 24 or PET or tissue
Solid, without Risk Factors		
≤4		Optional (12)
>4 to ≤5		12
>5 to ≤8		6, 18
>8		3, 9, 21 to 24 or PET or tissue
Part-solid		
Solitary, solid component ≤5		3, 15, 27, 39
Solitary, solid component >5		3, tissue if persists
Multiple, solid component ≤5		3, 15, 27, 39
Multiple, solid component >5		3, tissue if persists and solid ≥5
Non-solid		
≤5, solitary		None
>5, solitary		3, 15, 27, 39
≤5, multiple		24, 48
>5, multiple		3, 15, 27, 39

Table C2: Surveillance protocol for incidental nodules, Group B, Less intensive surveillance

Nodule characteristics	Surveillance times (months from index CT)
Solid	
<6, solitary or multiple	None (Optional at 12 months in patients with risk factors)
≥6 to ≤8, solitary	12, 24
≥6 to ≤8, multiple	6, 18
>8, solitary or multiple	3, 15, 27 or PET or tissue
Part-solid	
<6, solitary	None
<6, multiple	6, 24, 48
≥6, solid component <6	6, 18, 30, 42, 54, 66
≥6, solid component ≥6	6, tissue if persists
Non-solid	
<6, solitary	None
≥6, solitary	12, 36, 60
<6, multiple	6, 24, 48
≥6, multiple	6, 24, 48

Table C3: Surveillance protocols for screening-detected nodules

Lung-RADS Category	Nodule characteristics	Surveillance times (months from index CT)		
		Group A	Group B	
1	No nodule	12, 24...	12, 24...	
	Calcified nodule			
	Fat-containing nodule			
2	Solid nodule <4	12, 24...	12, 24...	
	Solid nodule <6	6, 18, 30...		
	New solid nodule <4			
	Part-solid nodule <6			
	Non-solid nodule <20			
	Non-solid nodule ≥20, unchanged or slow-growing			
	Category 3 or 4 nodule unchanged for >3 months			
3	Solid nodule ≥6 to <8	3, 15, 27...	6, 18, 30...	
	New solid nodule, ≥4 to <6			
	Part-solid nodule ≥6, with solid component <6			
	Part-solid nodule, new <6			
	Non-solid nodule ≥20			
4A	Solid nodule ≥8 to <15	3, 9, 21... (PET may be used when solid component ≥8)	3, 15, 27... (PET may be used when solid component ≥8)	
	Solid nodule, new ≥6 to <8, or growing <8			
	Part-solid nodule ≥6, with solid component ≥6 to <8			
	Part-solid nodule, new or growing, with solid component <4			
	Endobronchial nodule			
4B	Solid nodule ≥15	CT at 3 months, PET or tissue, depending on probability of cancer and comorbidities		
	Solid nodule, new or growing ≥8			
	Part-solid nodule, with solid component ≥8			
	Part-solid nodule, new or growing, with solid component ≥4			
4X	Category 3 or 4 nodules with additional features that suggest cancer	CT at 3 months, PET or tissue, depending on probability of cancer and comorbidities		

*Note: Patients with nodules described in boxes with gray shading are NOT eligible for Watch the Spot

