The original protocol for more intensive imaging was based on published guidelines from the Fleischner Society (2005, 2013) and the National Comprehensive Cancer Network (NCCN), while most of the recommendations for less intensive imaging were derived from the American College of Radiology's Lung CT Screening Reporting and Data System (Lung-RADS). However, Fleischner Society and NCCN recommendations were recently revised, providing an ideal opportunity to compare the (more intensive) existing recommendations with the (less intensive) newly revised recommendations, a comparison that is most relevant to current clinical practice.

The surveillance protocols are summarized in Tables 2 and 3. Additional details are provided in Appendix Tables C1-C3.

Table 2: Group A, More Intensive Surveillance					
Nodule characteristics	Nodule size (mm)	Surveillance times (months from index CT)	Optional	For screening-detected nodules (if different)	Source
Solid	≤4	12		12, 24	
	>4 to ≤6	6, 18			Fleischner, 2005
	>6 to ≤8	3, 9, 24		3, 9, 21	
	>8	3, 9, 24	PET/CT, biopsy	3, 9, 21	
Solitary Part-Solid	Any size, solid component ≤5	3, 15, 27, 39			
	Any size, solid component ≥5	3 (If persists, biopsy or resect)			Fleischner, 2013
Solitary Non-solid (GGN)	<5	None		12, 24	
	>5	3, 15, 27, 39			Fleischner, 2013
Multiple Part- or Non-solid	≤5 GGN	24, 48			
	>5 GGN	3, 15, 27, 39			Fleischner, 2013
	“Dominant”	3 (If persists, biopsy or resect)			

Table 3: Group B, Less Intensive Surveillance

Nodule characteristics	Nodule size (mm)	Surveillance times (months from index CT)	Optional	For screening-detected nodules (if different)	Source
Solid	<6	None	12	12, 24	Fleischner (2017)
	≥6 to ≤8	12, 24			
	>8	3, 15, 27	PET/CT, biopsy		
Part-solid	<6	None		12, 24	Fleischner (2017)
	≥6 with solid component <6	6, 18, 30			
	≥6 with solid component ≥6	6 (if persists, biopsy or resect)			
Non-solid	<6	None		12, 24	
	≥6	12, 36		12, 24	
Multiple	Solid, largest <6	None	12	12, 24	
	Solid, largest ≥6	6, 18			
	Part- or Non-solid	6, 24	6 (If persists, biopsy or resect)		

The comparators selected will result in approximately 30% less imaging in the less intensive Group B. By using these guidelines as the foundation for the surveillance protocols to be compared, we will preserve the trial's equipoise, integrity and relevance now that the revised Fleischner Society recommendations have been released⁴⁸.

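### For some nodule types, Tables 2 and 3 and Appendix C state conflicting scan schedules, and no rule says which one adherence is scored against

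*Combined protocol and SAP*

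**What the plan says.** The section on the interventions to be compared presents Tables 2 and 3 as a summary and refers to Appendix Tables C1 to C3 for further detail. It does not say which prevails if they differ.

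- **Group B, multiple solid nodules.** Table 3 has a row "Solid, largest ≥6" with no upper size limit, at 6, 18 months. Table C2 gives 6, 18 only to "≥6 to ≤8, multiple". For solid nodules ">8, solitary or multiple" it gives "3, 15, 27 or PET or tissue".
- **Screening-detected solid nodules.** Tables 2 and 3 have a column headed "For screening-detected nodules (if different". Table 2 enters 3, 9, 21 there for Group A, >6 to ≤8 mm. Table 3 has no separate entry for Group B, ≥6 to ≤8 mm, so its general schedule of 12, 24 applies. Table C3 category 3, "Solid nodule ≥6 to <8", gives Group A 3, 15, 27 and Group B 6, 18, 30. Category 4A includes new solid nodules of the same size band and gives 3, 9, 21 and 3, 15, 27.

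The Aim 4 outcomes section scores adherence against the recommended tests. The list of primary endpoints includes patient adherence to the first recommended exam and to the full protocol. The H1a analysis plan uses the same definitions for its on-treatment sensitivity analyses.

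**The concern.** The schedule is the randomised intervention. It is inserted into the radiology report through templates, and it is the yardstick for adherence by radiologist, ordering provider and patient. Where two current tables give different months for the same patient, that yardstick takes two values: someone who follows one table exactly can be non-adherent by the other. H4 compares adherence between arms, and the ambiguity is not symmetric. For screening-detected solid nodules between 6 and 8 mm, the Group A first exam is at month 3 in every table, while the Group B first exam is at month 12, 6 or 3. For these nodules, the choice of table can therefore change first-exam adherence in Group B alone.

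**Working it through.** The plan states no figure that can be reproduced here, so the check sets the rows side by side. The inputs are the printed months in Tables 2, 3, C2 and C3. For each pair I took the first scheduled month, the number of scans due at or before month 24, and the months common to both up to month 24. For the screening rows I used only the overlap of the size bands: Table 2's row starts above 6 mm and Table C3's band stops below 8 mm.

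| Arm and nodule | Body table | Appendix C | First scan (body v appendix) | Scans by month 24 | Shared months |
|---|---|---|---|---|---|
| B, multiple solid, largest >8 mm | Table 3 multiple row: 6, 18 | C2: 3, 15, 27 | 6 v 3 | 2 v 2 | none |
| B, screening solid 6 to <8 mm, category 3 | Table 3: 12, 24 | C3: 6, 18, 30 | 12 v 6 | 2 v 2 | none |
| B, same, category 4A (new) | Table 3: 12, 24 | C3: 3, 15, 27 | 12 v 3 | 2 v 2 | none |
| A, screening solid >6 to <8 mm, category 3 | Table 2: 3, 9, 21 | C3: 3, 15, 27 | 3 v 3 | 3 v 2 | 3 |
| A, same, category 4A (new) | Table 2: 3, 9, 21 | C3: 3, 9, 21 | 3 v 3 | 3 v 3 | all |

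**Row 1.** Table 3 also disagrees with itself. Its solid >8 mm row is not limited to solitary nodules and gives 3, 15, 27, as Table C2 does. The clash comes from the multiple-nodule row, which lacks the 8 mm ceiling that Table C2 applies.

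**Rows 2 and 3.** Group B differs from Table 3 whichever category of Table C3 applies. The comparison uses Table 3's solid block. A screening patient with multiple solid nodules would come under the 6, 18 row instead, which agrees with category 3 up to month 24.

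**Rows 4 and 5.** Whether Group A conflicts depends on what new means in Table C3. The trial enrols only newly identified nodules, but the protocol does not say whether that makes them new in the sense of category 4A.

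**Contrast between arms in first scan, screening solid, about 6 to 8 mm:**

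- Tables 2 and 3: 12 − 3 = 9 months.
- Table C3, category 3: 6 − 3 = 3 months.
- Table C3, category 4A: 3 − 3 = 0 months.

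**Other rows for the reconciliation.** The category 4A row "Part-solid nodule ≥6, with solid component ≥6 to <8" gives Group B 3, 15, 27, while Table 3 gives a single scan at 6 months with tissue if the nodule persists. Table C1's split under "Solid, without Risk Factors" changes Group A from 3, 9, 24 to 6, 18 for nodules >6 to ≤8 mm. Several Group B subsolid rows differ only by added scans after month 26, for example 6, 18, 30 against the same plus 42, 54, 66.

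**The case against.** The strongest reply is that the body tables are declared summaries and the appendix supplies the detail, so Table C2 merely splits Table 3's broad multiple-nodule row at 8 mm. That reading is reasonable for multiple nodules, and Table 3's own >8 mm row supports it. It can also explain the risk-factor split in Table C1 and the late scans in Table C2. It does not explain why 12, 24 becomes 6, 18, 30 or 3, 15, 27, because those months are replaced and not elaborated. Nor does the protocol say that the appendix governs.

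A second reply is extraction damage. Table C3 has merged cells, and its grey shading, which marks ineligible rows, is lost. The category 4A entries depend on reading one merged cell across the category, and row eligibility cannot be confirmed from shading. The category 3 row prints its size band and both schedules on one line, however, and Table 2's separate screening entry for >6 to ≤8 mm shows that such patients were expected. Table 3's screening cell yields 12, 24 whether it is blank or merged with the 12, 24 above it.

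Third, radiologists may tailor the templates and providers may deviate. That is departure from an assigned schedule; it does not identify the assigned schedule.

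A reader might infer more than the documents support:

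- *The intervention is undefined.* It is defined twice, in conflict, for some rows; many rows agree.
- *The first-scan contrast falls from 9 months to 3.* That holds only if category 3 applies; under category 4A it is 0, and Group A then matches Table 2 exactly.
- *Sites delivered different schedules.* Nothing shows this. The study supplies the templates to hospitals, which suggests a common source.
- *The primary result is compromised.* The main Aim 1 analysis is by assigned arm and uses no adherence definition.

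**Conclusion.** The conflict stands in the current text. For Group B it affects multiple solid nodules above 8 mm (6, 18 against 3, 15, 27) and screening-detected solid nodules of 6 to <8 mm (12, 24 against either of two Table C3 schedules). In both cases the first-exam date differs and no month up to 24 is shared. For Group A screening-detected solid nodules >6 to <8 mm, the conflict is conditional on how Table C3's new category relates to the eligibility criterion.

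The consequence falls on the Aim 4 primary adherence endpoints, on the H4 comparison between arms, and on the Aim 1 on-treatment and adherent-versus-non-adherent analyses. Its size cannot be given, because the documents do not report how many patients fall in these rows. Two facts limit its reach: screening-detected nodules are enrolled at only some of the 14 systems (six in the inclusion criteria, seven in Table 1), and radiologists may exclude patients with multiple nodules. The conclusion assumes that the printed months in the rows used were extracted correctly and, for category 4A, that its schedule cell covers the whole category.

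**What to change.** Reconcile Tables 2 and 3 with Tables C1 to C3 row by row. The choice of months belongs to the sponsor. At the same time:

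- State how Table 3's multiple-nodule row relates to its solid >8 mm row.
- Define new in Table C3 in relation to the newly identified eligibility criterion.
- Say which table governs the radiology templates and the scoring of adherence.
- Confirm what each site's template contained, and score adherence against that schedule. If adherence has already been scored, report which table was used and repeat the affected rows under the other.
- Report the number of patients per arm in the conflicting rows, so that readers can judge the effect.

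The cost is a protocol clarification, a check of the site templates and, if needed, one rerun of the adherence derivation. No new patient data are required.
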